Appendix A: Scientific Registry of Transplant Recipients

Program Summary: MUSC

Medical University of South Carolina

Center Code: SCMU

Transplant Program (Organ): Liver Release Date: January 5, 2018

Based on Data Available: October 31, 2017

SRTR Program-Specific Report Feedback?: [contact] [name] http://www.srtr.org

A. Program Summary

Figure A1. Waiting list and transplant activity

[figure not shown]

Table A1. Census of transplant recipients

Recipients	07/01/2015- 06/30/2016	07/01/2016- 06/30/2017
Transplanted at this center	69	93
Followed by this center*	658	658
transplanted at this progran	n 620	614
transplanted elsewhere	38	44

^{*} Recipients followed are transplant recipients for whom the center has submitted a post-transplant follow-up form for a transplant that took place before the 12-month interval for each column.

Figure A2. Transplant rates 07/01/2015 - 06/30/2017

[figure not shown]

Figure A3. Waiting list mortality rates 07/01/2015 - 06/30/2017

Figure A4. First-year adult graft and patient survival: 07/01/2014 - 12/31/2016

[figure not shown]
[figure not shown]

Figure A5. First-year pediatric graft and patient survival: 07/01/2014 - 12/31/2016

Appendix B: Patient Global Impression of Improvement (PGI-I)

Record ID	
Check the box that best describes how your tremor is now, compared to how it was before your liver transplant: * must provide value	Very much better Much better A little better No change A little worse Much worse Very much worse
Check the box that best describes how your headaches are now, compared to how they were before your liver transplant: * must provide value	Very much better Much better A little better No change A little worse Much worse Very much worse
Check the box that best describes how your insomnia (can't sleep) is now, compared to how it was before your liver transplant: * must provide value	Very much better Much better A little better No change A little worse Much worse Very much worse
Check the box that best describes how your paresthesias (tingling or numbness) is now, compared to how it was before your liver transplant: * must provide value	Very much better Much better A little better No change A little worse Much worse Very much worse

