Title:

The effect of conversion to once-daily Envarsus® on the neurologic toxicity burden in liver transplant recipients

Institution:

Medical University of South Carolina

Principal Investigators:

[name]

Office: [contact] [contact] Email: [contact]

1) Study Objectives

- a) Primary objective
 - i) Estimate the change from baseline to six months in neurotoxicity burden measured by a composite Patient Global Impression of Improvement (PGI-I) (Appendix B) score in patients converted to Envarsus daily ± adjunctive agent ± prednisone versus patients maintained on a standard therapy of Tacrolimus IR BID ± adjunctive agent ± prednisone

b) Secondary objectives

i) Estimate the change in the mean Fahn-Tolosa-Marin (FTM) score in patients with selfreported tremor from baseline to 6 months after enrollment

c) Exploratory Outcomes

- Examine subject specific change of self-reported adherence using the IMAB-Q 10 (Appendix C) at the time of the conversion versus six months post-conversion, compared between the two arms
- **ii)** Examine subject specific change in quality of life, using the SF-12 at the time of conversion versus six months post-conversion, compared between the two arms
- **iii)** Examine subject specific change in memory, using the Medical Symptom Validity Test, at the time of conversion versus six months post-conversion, compared between the two arms
- **iv)** Examine subject specific change in cognition, using the MoCA (Appendix E), at the time of conversion versus six months post-conversion, compared between the two arms
- v) Examine subject specific change in cognition, using the MMSE, at the time of conversion versus six months post-conversion, compared between the two arms
- vi) Measure and compare time-to-event analysis of secondary objective between the two arms
 - (1) Patient death (time to event analysis)
 - (2) Biopsy proven acute rejection (Banff RAI ≥ 5, time to event analysis)
 - (3) Graft loss (time to event analysis)
- vii) Compare rates of adverse events and severe adverse events between the two arms
- viii) Examine subject specific change in renal function, using the 4 variable MDRD, at the time of conversion versus six months post-conversion, compared between the two arms

2) Background

a) Rationale

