Diabetes	21 (43)	16 (15)				

ADRs in Multicenter Prospective, Randomized U.S. Trial

•		
	Tacrolimus	Cyclosporine/AZA
	(n=250)	(n=250)
Headache	64%	60%
Insomnia	64%	68%
Tremor	56%	46%
Paresthesia	40%	30%

3) Study interventions

- a) Interventions, administration, and duration
 - i) Subjects will receive the current standard of care for up to 15 days and no longer than 1 year post-transplant. Standard of care is described as a regimen of tacrolimus IR (goal 12 hour trough: 3-10ng/mL) BID ± adjunctive agent ± prednisone. Subjects are randomized to one of the two arms to either receive their standard of care regimen or convert their tacrolimus IR BID to Envarsus QD
 - (1) Both products FDA approved for preventing rejection in kidney transplant and are used as a standard of care for all organ transplants
 - ii) Post-randomization, subjects will be converted to one of the two arms, as shown below, and followed for a total period of six months (primary endpoint), or until a terminal end point is reached.
 - (1) Arm 1: Control-- Tacrolimus IR (goal 12 hour trough: 3-10ng/mL) BID ± adjunctive agent ± prednisone x 6 months
 - (2) Arm 2: Intervention-- Envarsus (goal 24 hour trough: 3-10 ng/mL) daily ± adjunctive agent ± prednisone x 6 months

- (a) Envarsus will be supplied from Veloxis Pharmaceuticals
- b) Neurotoxicity assessment
 - Changes in neurotoxicity comorbidity burden will be assessed at all study visits noted on the Schedule of Evaluations, using the composite score from applying the PGI-I score to tremor, headache, insomnia, and paresthesia.

4) Study Endpoints

- i) Primary outcome- Treatment efficacy, defined difference in change from baseline to six month measure by composite PGI-I in both arms.
- ii) Secondary outcomes
 - (a) Change in the FTM score in patients with self-reported tremor between baseline and six months post-enrollment in both arms
- iii) Exploratory outcomes
 - (1) Safety outcomes of treatment failure rate, defined as acute allograft rejection with a Banff RAI 5 or higher, graft loss, death, adverse events, or severe adverse events at six months post-conversion in both arms.
 - (2) Change in self-reported medication adherence, defined as the IMAB-Q10, between baseline and six months post-conversion in both arms
 - (3) Change in the subject specific quality of life, defined as the SF-12, between baseline and six months post-conversion in both arms

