 - (4) Change in subject specific memory, defined as the MSVT, between baseline and six months post-conversion in both arms
 - (5) Change in subject specific cognitive function, defined as the MoCA, between baseline and six months post-conversion in both arms
 - **(6)** Change in subject specific renal function, defined as the 4 variable MDRD, between baseline and six months post-conversion in both arms

5) Inclusion & Exclusion Criteria

- i) Potentially eligible patients will be screened by the PI and study coordinator using inclusion and exclusion criteria below to determine if they qualify for the study.
- ii) Inclusion criteria
 - (1) Male or female adult (≥18 years old) with a history of liver or liver/kidney transplant within 15 days to 12 months of transplant.
 - (2) Patients must be capable of understanding the purposes and risks of the study and have the ability to give written informed consent and be willing to participate and comply with the study. For those that consent virtually, subjects must be willing and able to use the Doxy.me platform and complete assessments virtually.
- iii) Exclusion criteria
 - (1) Patients will be excluded if they are pregnant or nursing females or males with a pregnant female partner
 - (2) HIV positive (HIV ab +)
 - (3) Unable to tolerate oral medications
 - (4) Use of another investigational product within thirty days prior to receiving study medication
 - (5) Moderate acute cellular rejection (RAI ≥ 5) within the past month
 - **(6)** A condition that is known to cause tremor such as essential tremor, Parkinson disease, or enhanced physiologic tremor.
 - (7) Patients taking medications known to induce tremors or dopamine blocking agents

(8) A condition or disorder that, in the opinion of the investigator, may adversely affect the outcome of the study or the safety of the subject

6) Number of Subjects

a) There will be 15 subjects in each arm, 30 subjects total

7) Setting Where Research Will Be Conducted

a) Study activities, including consent, enrollment, and randomization, will occur in the Liver Transplant Clinic at the Medical University of South Carolina or through Doxy.me.

8) Recruitment Methods

- a) Study enrollment procedures

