 - (1) No deviations from or changes to the study protocol should be initiated except when necessary to eliminate immediate hazard to the subject. However, the IRB and Study Sponsor must be informed of this as soon as possible thereafter. It is the PI's responsibility to report SAEs occurring during the study to the IRB, as required and as soon as possible.

10) Study design

- i) Single-center, open-label, randomized comparative trial for a duration of 6 months.
- ii) There will be 15 subjects in each arm, with a total study size of 30 subjects.
- **b)** Allocation: Three random permuted-blocks of ten, with equal arm allocation ratio will be used. In each block, REDCap will be used to ensure 1:1 randomization, with resulting 1:1 allocation in the overall cohort.
- c) Intervention Model: Parallel assignment
- **d)** Masking: This will be an open-label study as masking is not feasible given we are comparing twice-a-day to once-a-day regimen.
- e) Timing of evaluation
 - i) Pre-Randomization Evaluations
 - 1. Baseline
 - Evaluations listed under the baseline visit may be performed up to 14 days prior to randomization. Once the subject has been successfully screened and accepted for randomization, randomization must be completed within 48 hours.
 - ii) Intervention and Evaluations
 - Once the subject has been successfully randomized, study medication will be picked up from IDS by the study team to be dispensed to the subject or study medication will be shipped to the subject by IDS. Study evaluations must take place within the time window indicated on the Schedule of Evaluations (Section 3)
- f) Clinical and laboratory evaluations

i) Schedule of evaluations

Data Collection Schedule

	Baseline	Baseline Days Post-Conversi					on			
Report Form			7±2	14±3	30±5	60±7	90±10	120±10	150±10	180±10
Informed Consen	t Obtained ^{vi}	Х								
Randomization		Х								
Review of Inclusion	on and Exclusion Criteria	Х								
Medical History		Х								
Liver Transplant F	Recipient	Х								
Review of Medica	ations and Dosing	Х								Х
Clinical assessment* Adverse events, rejection, graft loss, death						х			х	
	PGI-I, IMAB-Q 10, MSVT, MoCA, and SF- 12, MMSE ^v	х								х
	Fahn-Tolosa-Marin ^{iv}	Х								Х
Laboratory	CBC and Chem-7 ⁱ	0	0	0	0	0	0	0	0	0
Assessments	LFTs ⁱⁱ	0	0	0	0	0	0	0	0	0
	Tacrolimus CO ⁱⁱⁱ	0	0	0	0	0	0	0	0	0
End of Study										Х

X=required; 0=optional: data will be collected if performed as standard of care Footnotes:

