- i) Includes sodium, potassium, chloride, CO2, BUN, SrCr, glucose, calcium, WBC, HgB, Hct, platelets
- ii) Includes AST, ALT, alkaline phosphatase, total bilirubin, albumin, total protein
- iii) Tacrolimus concentrations will be 12- or 24-hour levels, drawn in the morning of each assessment
- iv) Only required for patients with self-reported tremor
- v) MSVT,MMSE, MoCA, FTM will be completed through a Doxy.me visit. PGI-I, IMAB-Q 10 and SF-10 will be sent to the subject through REDCap to be completed. Necessary materials (ball point pen and paper) to complete the MoCA, MMSE, and FTM will be shipped to the subject prior to the Doxy.me visit.
- vi) For subjects consented through Doxy.Me, this will be done prior to the baseline visit with the assessments.

11) Specimen Collection and Assessments

- i) Clinical and Laboratory Assessments:
 - (1) Laboratory evaluations will be performed at certified laboratories according to the study schedule. Required tests are specified in the Schedule of Evaluations. Laboratory

- specimens will not be stored for the study or sent to any outside facilities. Specimens will not be used for future research.
- (2) All subjects will undergo clinical assessment by the investigator or the investigator's designee in the manner and at the times specified in the Schedule of Evaluations
 - (a) Adverse events will be determined and defined according to the protocol
 - (b) Doses will be recorded of all immunosuppressants.
 - (c) Rejection and infection events will be recorded, as defined in the protocol
- (3) Renal function assessment will be monitored at regular intervals using the 4-variable abbreviated MDRD equation. It will be monitored at baseline and the end of the study for study outcomes and any time points dictated by standard of care follow-up in between those time points.
- ii) Definitions
 - (1) Acute rejection is defined as a liver allograft biopsy showing RAI 5 or greater, by the 1997 Banff Criteria and all updates since then. Biopsies will be performed when clinically warranted, based on changes in allograft function.
 - (2) Rejection reversal is defined as return of liver function tests to within 20% of baseline and/or histologic clearance by Banff Criteria
 - (3) Recurrent acute rejection is defined as rejection recurring more than two weeks after documented rejection reversal.
- iii) Treatment of Acute rejection:
 - (1) Acute rejection will be treated per provider discretion.
- iv) Opportunistic Infections

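### The primary PGI-I rates symptoms against the time before transplant, not study baseline, and the sample size figures are not tied to any stated scoring of it

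*Combined protocol and SAP*

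**What the plan says.** The primary outcome in section 4) i) is "Treatment efficacy, defined difference in change from baseline to six month measure by composite PGI-I in both arms", and the primary objective in section 1) a) is worded to match. Section 3) b) forms the composite from tremor, headache, insomnia and paresthesia.

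Appendix B holds the only PGI-I form. The tremor item reads "Check the box that best describes how your tremor is now, compared to how it was before your liver transplant", and the other three use the same reference point. The answers are seven categories from very much better, through no change, to very much worse. The Data Collection Schedule in section 10) f) marks the row with "PGI-I, IMAB-Q 10, MSVT, MoCA, and SF- 12" at baseline and at day 180±10.

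Patients enter "with a history of liver or liver/kidney transplant within 15 days to 12 months of transplant". On timing, section 10) e) adds: "Evaluations listed under the baseline visit may be performed up to 14 days prior to randomization".

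Section 12) c) sizes the trial on a neurologic toxicity burden score. It expects 45 at baseline, 45 ± 20 at baseline and follow-up on tacrolimus IR, and 25 ± 15 at the end on Envarsus. The 45 is said to rest on reported rates of headache (64%), insomnia (64%), tremor (56%) and paresthesia (40%). No section gives item scores, a rule for combining the items, or a range for the composite.

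**The concern.** There are two separate points.

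**Anchor.** The endpoint asks how the patient has changed since study baseline. The form asks, twice, how the patient compares with a time before the transplant. The answer to the first question has to be obtained by subtracting two answers to the second, each relying on memory of an event that lies a different distance back for each patient.

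**Scale.** A better/worse rating is not a level of burden. A patient who never had the symptom and a patient with the same symptom before and after transplant both tick *no change*. The sample size section nevertheless uses levels, and takes the baseline level from percentages of patients with each reaction. This would be so whichever reference point the form used.

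At stake is whether the primary result answers the stated objective directly, and whether the stated power describes the endpoint that will be analysed.

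**Working it through.** **1. The plan's sample size.** Inputs from section 12) c): means 25 and 45, SDs 15 and 20, two-sided alpha 0.05, two-sample t-test.
- Pooled SD = √((15² + 20²)/2) = √312.5 = 17.68.
- Standardised difference = 20/17.68 = 1.13.
- By the noncentral t distribution, power is 0.790 at 13 per arm, 0.822 at 14 and 0.849 at 15.

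The stated 14 per group is reproduced. The arithmetic is sound; the question is what scale it is on.

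**2. Source of the 45.** (64 + 64 + 56 + 40)/4 = 224/4 = 56. The step from these rates to 45 is not shown.

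**3. What 45 and 25 would mean.** The scoring is not stated, so each line below is an assumption, and the list is not claimed to be complete.

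| Assumed scoring | Formula | 45 | 25 |
|---|---|---|---|
| (a) Sum of four items, each 1–7 | range 4×1 to 4×7 = 4 to 28; largest SD (28 − 4)/2 = 12 | impossible | possible |
| (b) 0–100, higher = worse | category = 1 + 6s/100; *no change* (4) is s = 50 | 3.7, slightly better than before transplant | 2.5, midway between *much better* and *a little better* |
| (c) 0–100, higher = better | category = 7 − 6s/100 | 4.3 | 5.5, so 45 to 25 is a worsening |
| (d) 0–100, only worsening counted | steps worse = 3s/100 | 1.35 | 0.75 |

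Under (a) the assumed SDs of 15 and 20 also exceed the largest possible SD. Scoring items 0–6 or −3 to +3 gives sums of 0 to 24 or −12 to +12, with the same maximum SD of 12 and the same conclusion. Of the four, only (d) reads as section 12) c) intends, and there the 20-point difference is 1.35 − 0.75 = 0.6 of a category. Under (b) and (c) it is 6 × 20/100 = 1.2 categories.

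**4. How far back the question reaches.** Inputs: entry at 15 to 365 days after transplant (12 months taken as 365 days), baseline up to 14 days before randomization, final visit at day 170 to 190, and no gap between randomization and first dose (none is given).
- Baseline, transplant anchor: 15 to 365 days.
- Day 180, transplant anchor: 15 + 170 = 185 to 365 + 14 + 190 = 569 days; spread 384 days.
- Day 180, study-start anchor: 170 to 14 + 190 = 204 days; spread 34 days.

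These are elapsed times, not measured recall error.

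**The case against.** The best defence of the anchor is that it is deliberate. Section 2) frames the problem as neurotoxicity associated with tacrolimus after transplant, and a comparison with the time before transplant sets aside symptoms that predate the drug. The anchor is also the same event for a given patient at both visits, so any stable error in recalling it cancels in the change score; only unstable recall adds noise. Both points stand. The documents also do not show that patients recall study start more accurately than the time before transplant.

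A reader might infer that the endpoint carries no information on change since baseline. It does carry some, because the two ratings share an anchor. A reader might also infer that the wording favours one arm. Nothing shows this: the baseline rating precedes randomization, and the influence of known treatment on the day-180 rating would apply to any unmasked self-report.

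On the scale, a reader might infer that the score can never represent a fall from 45 to 25. Scoring (d) shows otherwise. It is also fair to say that the mismatch comes from the missing scoring and the incidence-based inputs, not from the anchor; a study-start item would give no level either.

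Replacing the form outright would have a cost: it would discard the one rating made before allocation. The tremor scale already gives current severity at both visits for patients with self-reported tremor, but it does not cover headache, insomnia or paresthesia.

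**Conclusion.** Two limited conclusions hold.

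- The primary endpoint reflects change since study baseline only indirectly, through two recalled comparisons with the time before a transplant that took place 15 days to 12 months before entry. The look-back at day 180 varies by 384 days between patients, against 34 with a study-start anchor. The documents do not allow the effect on precision to be quantified, and they show no bias.
- Whatever the anchor, it cannot be determined whether 45 and 25 fit the instrument. On a plain four-item sum, 45 and both SDs are impossible; on the 0–100 scalings the meaning ranges from slight improvement to moderate worsening since transplant. The power above 80% is therefore not shown to apply to this endpoint.

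This does not establish that the true power is below 80%; it is unknown. The scale readings rest on assumed scorings, and the look-back figures rest on the visit windows and a zero gap to first dose.

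The change is worth making because it is cheap and lets the form ask the question that the objective poses.

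**What to change.** 1. At day 180, add four items worded *compared to how it was when you started this study* to the PGI-I form already sent through REDCap (section 10) f), footnote v). Keep the pre-transplant items at both visits. Make the between-arm comparison of the re-anchored composite the primary analysis, using the two-sample t-test already named. As a supporting analysis, compare the pre-transplant composite at day 180 adjusted for its baseline value. This analysis retains the rating made before allocation and covers any patient already past day 180.
2. State the scoring, for example the mean of the four items with 1 = very much better, 4 = no change and 7 = very much worse. Withdraw the 45 and 25 figures and restate section 12) c) as the difference detectable with 14 to 15 per arm, giving the SD as an assumption with a range. For illustration, 1.13 SD has power 0.822 at 14 per arm and 0.849 at 15. With assumed SDs of 0.5, 1.0 and 1.5 categories, that is 1.13 × SD = 0.57, 1.13 and 1.70 categories.
3. Reword sections 1) a) and 4) i) as patient-rated change since study baseline.

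**Cost.** Four extra questions at one visit and an amendment; no added visit. If enrolment has begun, patients already past day 180 lack the new rating and contribute only to the supporting analysis. The margin is thin: on the plan's own inputs, power falls to 0.790 at 13 per arm.

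**What remains.** About six months of recall, unmasked self-report, and *no change* answers from patients without the symptom, since entry does not require any.

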Appendix C: IMAB-Q10 Questionnaire

People have different experiences of trying to take their medicines as prescribed (right dose and right time). We understand that things can 'get in the way' of following your doctor's recommendations about taking your medicines. This questionnaire lists 10 different statements about taking your medicines.

	Statement	Strongly agree	Agree	Neither agree nor disagree	Disagree	Strongly disagree
1	I know how to take my					
	medicines as prescribed					
2	I am physically able to take					
	my medicines as prescribed					
3	I remember to take my					
	medicines as prescribed					
4	I can easily get hold of my					
	prescribed medicines from					
	the pharmacy or surgery					
5	I feel confident about all					
	aspects of managing					
	(ordering, collecting and					
	taking) my medicines					
6	I worry about the unwanted					
	effects (e.g. harmful effects					
	or side effects) of taking my					
	medicines					
7	Taking my medicines as					
	prescribed is a burden to me					
8	Life gets in the way of me					
	taking my medicines as					
	prescribed					
9	I don't think I could cope if					
	my medication regime kept					
	changing					
10	I worry about what other					
	people would think of me if					
	they knew I took medicines					

